4.4. Secondary outcome measures

Secondary outcomes are as follows:

- Individual components of the primary outcome
- All-cause mortality within 3 hours of randomisation
- All-cause mortality within 30 days of randomisation
- Pre-hospital time and type and volume of fluid
- Vital signs (systolic blood pressure, heart rate, capillary oxygen saturation) at scene, on arrival at the ED, then also at 2, 6, 12 and 24 hours after arrival at ED
- Haemoglobin concentration on ED arrival

- (Venous) lactate concentration on arrival at ED and at 2 hours after arrival at ED
- Trauma-induced coagulopathy (defined as International Normalised Ratio (INR) >1.5) to be measured on arrival at ED, and also at 2 and 6 hours after arrival at ED
- Total blood product receipt at 6, 12 and 24 hours after arrival at ED
- ARDS within the first 7 days after injury
- Transfusion-related complications
- Organ failure-free days The presence of organ failure is defined as any Sequential Organ Failure Assessment (SOFA) component score of ≥ 3 . Organ failure will be assumed to be absent if the participant is discharged from acute care and will be assumed to be present if the participant has died

At selected receiving hospital sites (RHS) the following secondary outcomes will also be recorded:

- Coagulation measured viscoelastically by rotational thromboelastometry (ROTEM[®])
- Platelet function using multiple electrode impedance aggregometry (MultiPlate)

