4.11. Timing of final analysis

The final analysis for the trial will occur once all the participants have completed the trial. The main trial data collection for participants ends at withdrawal, discharge to non-acute care, death or at 30 days follow-up, whichever occurs first. Apart from episode mortality data which is collected up to discharge from acute care which may be >30 days. Final analysis will then occur only after the corresponding outcome data has been entered onto the trial database and validated as being ready for analysis. This is provided that the trial has not been stopped early for any reason (e.g. DMC advice or funding body request).

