s2 2, then as per the table above the participant would be considered to have achieved clearance; or if both the randomisation and 2 hour lactates are OOR, then the participant will be considered to have failed to clear. If unable to determine, then the lactate component of the primary outcome will be considered missing.

Episode Mortality

Episode mortality is defined as those participants who die during the study between time of injury/recruitment and discharge from the primary receiving facility to non-acute care (this includes participants who die on-scene). The date of discharge from acute care and date of death are recorded on the exit form. Any deaths occurring after the date of discharge from acute care are not considered to be cases of episode mortality.

Primary Outcome

The primary outcome is a composite measure consisting of episode mortality (mortality between time of injury/recruitment and discharge from the primary receiving facility to non-acute care) and lactate clearance (failure to achieve lactate clearance $\geq 20\%$ per hour in the first two hours from randomisation). Therefore, if the participant experiences either:

- a) episode mortality or
- b) a failure to achieve lactate clearance $\geq 20\%$ per hour in the first 2 hours after randomisation

they will be considered to have experienced the primary outcome. If they have survived to the point of exiting the trial through discharge from acute care and have experienced lactate clearance $\geq 20\%$ per hour in the first 2 hours after randomisation they will be considered to not have experienced the primary outcome.

All-cause mortality within 3 hours of randomisation

The time to death is calculated by (Date and Time of death - Date and Time of randomisation). If this is less than or equal to 3 hours then the participant will be coded as having experienced all-cause mortality within 3 hours of randomisation (i.e. ≤ 3 hours). If this is more than 3 hours (i.e. >3 hours), or if the participant has completed the exit form through discharge from acute care then the participant will be coded as not having experienced all-cause mortality within 3 hours of randomisation. If the Date and Time of death is not recorded, but the participant is known to have died on-scene, then it will be assumed that the participant experienced all-cause mortality within 3 hours of randomisation.

All-cause mortality within 30 days of randomisation

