The time to death is calculated by (Date of death - Date of randomisation). If this is less than or equal to 30 days then the participant will be coded as having experienced all-cause mortality within 30 days of randomisation (i.e. ≤ 30 days). If this is more than 30 days (i.e. >30 days), or if the participant has completed the exit form through discharge from acute care (i.e. was alive at discharge from acute care) then the participant will be coded as not having experienced all-cause mortality within 30 days of randomisation. If the Date and Time of death is not recorded,

but the participant is known to have died on-scene, then it will be assumed that the participant experienced all-cause mortality within 30 days of randomisation

Trauma-induced coagulopathy

A participant is considered to have experienced trauma-induced coagulopathy if the INR > 1.5. If no INR value has been recorded, the value of prothrombin time (PT) will be converted to an INR value and used instead. To convert PT to an INR, the ratio of the observed patient PT to a control PT (standardized for the potency of the thromboplastin reagent) will be calculated:

This calculation requires the control PT to be known

Organ failure-free days (OFFS)

The presence of organ failure is defined as any SOFA component score of ≥ 3 . Organ failure will be assumed to be absent if the participant is discharged from acute care and will be assumed to be present if the participant has died.

The SOFA component scores are determined from the raw values using the conversions in Tables (a)-(f) below. For each daily assessment organ failure is present if:

ANY (Respiratory, Neurological, Cardiovascular, Liver, Coagulation, Renal) ≥ 3

PaO ₂ /FiO ₂ (kPa)	Score
≥ 53.3	0
<53.3	1
<40.0	2
<26.7 and mechanically ventilated	3
<13.3 and mechanically ventilated	4

Glasgow Coma Scale (GCS)	Score
15	0
13-14	1
10-12	2
6-9	3
<6	4

Mean Arterial Pressure or inotrope requirement	Score
MAP ≥ 70 mmHg	0
MAP <70 mmHg	1
dop ≤ 5 or dop (any dose)	2
dop >5 OR epi ≤ 0.1 OR nor ≤ 0.1	3
dop >15 OR epi >0.1 OR nor >0.1	4

Bilirubin ($\mu\text{mol/L}$)	Score
<20	0
20-32	1
33-101	2
102-204	3
>204	4

Key: dop: Dopamine, dob: dobutamine, epi: adrenaline, nor: noradrenaline
Doses in []g/kg/min

Coagulation (e)	
Plateletsx10 ³ /μl	Score
≥150	0
<150	1
<100	2
<50	3
<20	4

Renal (f)	
Creatinine (μmol/L) or urine o/p	Score
≤109	0
110-170	1
171-299	2
300-440 (or <500 mL/day)	3
> 440 (or <200 mL/day)	4

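### The 30-day mortality rule in SAP 9.4 counts everyone discharged alive from acute care as a 30-day survivor, so it measures mortality to acute-care discharge or day 30, whichever comes first, and not all-cause 30-day mortality as labelled

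*SAP*

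**What the plan says.** Section 4.4 lists "All-cause mortality within 30 days of randomisation" as a secondary outcome, and Appendix D7 reports it under that name with a relative risk, a risk difference and a p-value.

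Section 9.4 derives it from the interval between randomisation and death. The event clause reads: "If this is less than or equal to 30 days then the participant will be coded as having experienced all-cause mortality". The non-event clause has two routes: death after more than 30 days, "or if the participant has completed the exit form through discharge from acute care (i.e. was alive at discharge from acute care"). A further sentence counts a death known to have happened on scene as an event when its date and time are missing.

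On follow-up, section 4.11 says: "The main trial data collection for participants ends at withdrawal, discharge to non-acute care, death or at 30 days follow-up, whichever occurs first". It makes one exception: "Apart from episode mortality data which is collected up to discharge from acute care which may be >30 days".

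On the source of the dates, section 9.4 says under episode mortality: "The date of discharge from acute care and date of death are recorded on the exit form". It continues: "Any deaths occurring after the date of discharge from acute care are not considered to be cases of episode mortality".

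**The concern.** Being alive at discharge on, say, day 8 does not establish being alive on day 30. The rule treats it as if it did, and the follow-up described in the SAP collects nothing after discharge that would correct it. A fixed-time outcome thereby becomes one whose window closes at discharge for anyone who leaves acute care early.

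Three things are at stake. The label promises something that the derivation does not deliver, and a reader of the results table will not see the coding rule. The outcome also moves close to episode mortality: where no post-discharge death is counted, the two differ only by deaths in acute care after day 30. Finally, two programmers could code the same participant differently, because the event and non-event clauses overlap and no order of precedence is given.

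Nothing else in the SAP brings the assumption to light. Section 9.3 says that analysis uses received data, section 9.10 limits sensitivity analyses to the primary outcome, and D7 attaches no footnote on discharge to this row. By contrast, D7 gives 3-hour mortality a second, footnoted version restricted to participants with an exact time of death.

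**Working it through.** The SAP states no rate, power or sample size for 30-day mortality, so there is no figure to reproduce. The check is to apply the rule to test participants.

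**Inputs.** From 9.4: the event clause (death at 30 days or less) and the non-event clause (death after 30 days, or exit through live discharge). From 4.11: main data collection stops at discharge if that comes before day 30.

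**Two readings.** Reading A applies the event test first and treats it as final. Reading B applies the two sentences in written order, so that the second can replace the result of the first.

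| Test participant | True status at day 30 | Reading A | Reading B |
|---|---|---|---|
| Dies in acute care, day 10 | dead | event | event |
| Dies in acute care, day 45 | alive | non-event | non-event |
| Discharged day 8, alive at day 30 | alive | non-event | non-event |
| Discharged day 8, dies day 20, death not recorded | dead | **non-event** | **non-event** |
| Discharged day 8, dies day 20, death recorded | dead | event | **non-event** |
| Withdrawn day 5 | unknown | not coded | not coded |

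The fourth row is the main result. Where the death is not recorded, both readings code a 30-day death as survival, so the order of the clauses does not help. The fifth row shows the ambiguity: the text supports either code.

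**What is measured.** If post-discharge deaths are not recorded, or if reading B is used, an event requires death both before acute-care discharge and by day 30. If some are recorded and reading A is used, the variable is a mixture: acute-care deaths by day 30 plus whichever later deaths happen to be known.

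**Number of deaths missed.** Let m be acute-care mortality by day 30, s the share of the remainder discharged before day 30, and q the share of those who die between discharge and day 30. Then

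deaths missed = N × (1 − m) × s × q.

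Only N = 490 (section 4.7) is in the SAP. The other three values are assumptions, chosen wide: m from 20% to 40%, s from 50% to 80%, q from 1% to 5%.

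- Lowest: 490 × 0.60 × 0.50 × 0.01 = 1.5 deaths, or 0.3 percentage points.
- Highest: 490 × 0.80 × 0.80 × 0.05 = 15.7 deaths, or 3.2 percentage points.

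A tenfold range resting on three assumed inputs shows only how the quantity scales. It is not an estimate for this trial.

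**Effect on the relative risk.** If fractions f₁ (PHBP) and f₀ (crystalloid) of true 30-day deaths are coded as survivors, and no survivor is coded as dead, then

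coded RR = true RR × (1 − f₁) / (1 − f₀).

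When f₁ = f₀ the ratio is unchanged. When they differ it moves, in a direction that depends on which is larger. The SAP gives neither value.

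**The case against.** The strongest defence is that the rule is pre-specified, states its own assumption in brackets, and follows the same convention as organ failure, which the SAP takes as absent after discharge from acute care. The protocol, which holds the assessment schedule and is not shown here, may provide for vital status after discharge. The outcome is one secondary endpoint; the primary outcome and the power calculation are untouched. The same clause in the 3-hour rule does little harm, because live discharge within 3 hours is improbable.

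All of that limits the weight of the point, but it does not remove it. Pre-specifying a rule does not make the label accurate, and a day-30 check in the protocol would not help a derivation that codes by discharge without using it.

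A reader might infer four stronger things, and the SAP does not support them.

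- *That the rule overwrites known deaths.* This needs a recorded post-discharge death and also reading B. The more natural reading settles a death by day 30 first. The SAP foresees deaths after discharge when it excludes them from episode mortality, but it does not show that they are systematically collected. What stands is an unstated order of precedence.
- *That all unknown vital status is coded as alive.* Only live discharge from acute care triggers the clause. Withdrawal is a separate exit, and the rule does not code it as survival.
- *That the comparison is biased between arms, for example through earlier discharge or transfer.* Nothing in the SAP gives discharge timing or post-discharge deaths by arm, and nothing says that transfer to another acute hospital counts as discharge.
- *That a definite number of deaths is lost.* The SAP shows that 30-day mortality could be understated, but not by how much.

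Closely resembling episode mortality is also no error in itself, since 4.11 expressly provides for acute-care deaths after day 30.

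**Conclusion.** The point holds as a mismatch between label and derivation, together with an unstated precedence. On the data collection described in 4.11, the variable in 9.4 is mortality to discharge from acute care or day 30, whichever comes first. It should not be presented as all-cause mortality within 30 days. A participant discharged alive with a recorded death by day 30 satisfies both clauses, and the SAP does not say which one governs.

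Neither the number of deaths affected nor the size and direction of any effect on the relative risk can be determined from the document. The conclusion rests on the wording of 9.4 and 4.11 alone. If the protocol does secure day-30 status in both arms, the remedy becomes easier, but the rule as written still needs changing. The matter should be corrected before analysis, because this is a mortality result that readers will take at face value.

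**What to change.** Choose one of two alternatives according to what was collected.

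(a) If vital status at day 30 is obtained in both arms: state in 9.4 that a death on or before day 30 is an event whatever the discharge status, and treat unknown day-30 status as missing. The label can then stay.

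(b) If it is not obtained: keep the discharge rule, and rename the outcome in 4.4, 9.4 and Appendix D7 as *mortality to discharge from acute care or day 30, whichever comes first*. Footnote the assumption in D7, and do not report the result as all-cause 30-day mortality. State in 9.4 that deaths after discharge from acute care do not count, which settles the precedence.

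The two should not be combined. Counting only those post-discharge deaths that happen to be known would put events into the renamed outcome that its name excludes, and would make ascertainment uneven in an open-label trial.

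The cost is one line of derivation plus changes to a label and a footnote; (b) needs no new data. The drawback of (b) is a less familiar label that is harder to set beside other trials.

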4.2. Trial interventions

PHBP (Lyophilised Plasma LyoPlas N-w (LyoPlas) and PRBC) resuscitation vs crystalloid (0.9% sodium chloride [normal saline]) resuscitation (standard care)

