Then OFFS is the number of days alive and free of organ failure in the first 30 days. Days in which a participant is on a ward will be defined as being organ failure free. For the respiratory component, days in which a participant is either on a ward or in level 2 critical care will be defined as being ventilator free.

Age of Blood Products

For each participant allocated to the PHBP, the age of each unit of administered blood products is calculated by (Date bled - Date of randomisation). If any unit is 8 days or older, that participant will be classified as receiving blood products ≥8 days old for the purposes of the subgroup analysis (see Section 9.9).

Cardiac Arrest

Participants will be classified as experiencing cardiac arrest if they have a heart rate of 0 and a blood pressure reading (systolic or diastolic) of 0 when their vital signs are recorded on-scene.

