9.9. Planned subgroup analyses

Interpretation of subgroup analysis will be treated with caution (output will be treated as exploratory rather than definitive¹²). Analysis will be limited to the primary outcome of a composite measure consisting of episode mortality and lactate clearance only, and the following subgroups:

- IDS
- Mode of PHEM transport (air vs ground)
- Initial lactate concentration (≤ 2.2 mmol/L vs >2.2 mmol/L)

- Time to ED from injury (≤1 hour vs >1 hour)
- Mode of injury (blunt vs penetrating vs crush)
- Volume of pre-hospital fluid given (total intervention (4 boluses) vs <4 boluses)
- Age (<50 years, 50-70 years, >70 years)
- Head injury (positive vs negative)
- Compressible haemorrhage (compressible haemorrhage vs non-compressible haemorrhage)
- Pre-morbid drug history (anticoagulant or antiplatelet medication vs no anticoagulant or antiplatelet medication)
- Age of blood products (<8 days vs ≥8 days)
- Cardiac arrest (arrested vs not arrested)

The effects of these subgroups will be examined by including a treatment group by subgroup interaction parameter in the regression model. A template for reporting the subgroups analyses for the primary outcome is given in Appendix D9.

The anticipated magnitude and direction of differential treatment effects in each of the subgroup analyses are:

- IDS: regional differences in PHEM protocols and system characteristics may alter the effect of the intervention. However, the anticipated direction of effect is unclear in the subgroup analysis for IDS and this analysis will be regarded as purely exploratory.
- Mode of PHEM transport (air vs ground): ground transport typically takes longer than air transport, thus a greater effect of intervention may be observed in those being transported by ground.
- Initial lactate concentration (≤2.2 mmol/L vs >2.2 mmol/L): participants with an abnormal initial lactate concentration (>2.2 mmol/L) may have a higher incidence of the primary outcome event and may exhibit a greater benefit from PHBP.
- Time to ED from injury (≤1 hour vs >1 hour): participants taking >1 hour to arrive in ED from injury take longer to receive definitive treatment. Thus, a greater effect of intervention may be observed in participants taking more than >1 hour to arrive and receive definitive treatment in ED.

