- Mode of injury (blunt vs penetrating vs crush): the anticipated direction of effect is unclear in the subgroup analyses for mode of injury and this analysis will be regarded as purely exploratory.
- Volume of pre-hospital fluid given (total intervention (4 boluses) vs <4 boluses): the volume given is considered a surrogate for the volume of blood loss. Participants receiving <4 boluses of pre-hospital fluid may have experienced less blood loss and a lower incidence of the primary outcome event. Thus, they may exhibit a reduced effect from PHBP.
- Age (<50 years, 50-70 years, >70 years): mortality is greater in the more elderly groups. Therefore, the intervention is anticipated to have a greater effect in the >70 years cohort.

- Head injury (positive vs negative): Major haemorrhage increases the risk of secondary brain injury We anticipate that the intervention effect may be greater in those with head injury
- Compressible haemorrhage (compressible haemorrhage vs non-compressible haemorrhage): the anticipated direction of effect is unclear in the subgroup analyses for compressible haemorrhage and this analysis will be regarded as purely exploratory
- Pre-morbid drug history (anticoagulant or antiplatelet medication vs no anticoagulant or antiplatelet medication): the degree of haemorrhage will be greater in those with anticoagulation medication Therefore, we anticipate that the intervention may have a greater effect in those participants on anticoagulant medication
- Age of blood products (<8 days vs ≥8 days): fresh blood has better oxygen carrying capacity than old blood, therefore we anticipate that the intervention may have a greater effect in those participants receiving fresher blood (<8 days old)
- Cardiac Arrest: participants experiencing a cardiac arrest may have a higher incidence of the primary outcome event, but may be less likely to demonstrate any differential treatment effect due to the severity of their condition

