Appendix D9: Subgroup analysis for primary outcome

Subgroup description	PHBP (N=)	Crystalloid (N=)	Adjusted relative risk (95% CI) ¹	p-value for interaction
IDS				
Site 1	n (%)	n (%)	Relative risk (95% CI) ¹	p-value
Site 2	n (%)	n (%)	Relative risk (95% CI) ¹	
Site 3	n (%)	n (%)	Relative risk (95% CI) ¹	
Site 4	n (%)	n (%)	Relative risk (95% CI) ¹	
Mode of transport				
Air	n (%)	n (%)	Relative risk (95% CI) ¹	p-value
Ground	n (%)	n (%)	Relative risk (95% CI) ¹	
Initial Lactate Concentration				

s2.2 mmol/L	n (%)	n (%)	Relative risk (95% CI) ¹	p-value
>2.2 mmol/L	n (%)	n (%)	Relative risk (95% CI) ¹	
Cardiac Arrest				
Yes	n (%)	n (%)	Relative risk (95% CI) ¹	p-value
No	n (%)	n (%)	Relative risk (95% CI) ¹	
Time to ED from injury				
s 1 hour	n (%)	n (%)	Relative risk (95% CI) ¹	p-value
>1 hour	n (%)	n (%)	Relative risk (95% CI) ¹	
Mode of injury				
Blunt	n (%)	n (%)	Relative risk (95% CI) ¹	p-value
Penetrating	n (%)	n (%)	Relative risk (95% CI) ¹	
Crush	n (%)	n (%)	Relative risk (95% CI) ¹	
Volume of pre-hospital fluid given				
4 units	n (%)	n (%)	Relative risk (95% CI) ¹	p-value
< 4 units	n (%)	n (%)	Relative risk (95% CI) ¹	
Age				
<50 years	n (%)	n (%)	Relative risk (95% CI) ¹	p-value
50 - 70 years	n (%)	n (%)	Relative risk (95% CI) ¹	
>70 years	n (%)	n (%)	Relative risk (95% CI) ¹	
Head Injury				
Positive	n (%)	n (%)	Relative risk (95% CI) ¹	p-value
Negative	n (%)	n (%)	Relative risk (95% CI) ¹	
Compressible Haemorrhage				
Compressible Haemorrhage	n (%)	n (%)	Relative risk (95% CI) ¹	p-value
Non-Compressible Haemorrhage	n (%)	n (%)	Relative risk (95% CI) ¹	
Pre-morbid drug history				
Anticoagulant/antiplatelet medication	n (%)	n (%)	Relative risk (95% CI) ¹	p-value
No anticoagulant/antiplatelet medication	n (%)	n (%)	Relative risk (95% CI) ¹	
Age of blood products				
<8 days	n (%)	n (%)	Relative risk (95% CI) ¹	p-value
≥8 days	n (%)	n (%)	Relative risk (95% CI) ¹	

¹Output from log-binomial regression model. Values of relative risk <1 indicate lower rate of negative events (episode mortality or failure to clear lactate concentration) with PHBP.

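### Age of blood products is defined only in the PHBP arm, so its planned treatment interaction cannot be estimated; the age formula is also reversed

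*SAP*

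**What the plan says.** Section 9.4 of the SAP limits the derivation to one arm: "For each participant allocated to the PHBP", it says, "the age of each unit of administered blood products is calculated by (Date bled - Date of randomisation"). It then sets the classification: "If any unit is 8 days or older, that participant will be classified as receiving blood products ≥8 days old".

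Section 9.9 lists "Age of blood products (<8 days vs ≥8 days") among twelve subgroups for the primary outcome and says their effects will be examined by "including a treatment group by subgroup interaction parameter in the regression model". No subgroup is exempted. It expects more benefit with fresher units, because "fresh blood has better oxygen carrying capacity than old blood".

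Appendix D9 has a block headed "Age of blood products" with the same layout as the rest: a PHBP column, a crystalloid column, an adjusted relative risk for each of the two levels, and an interaction p-value.

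Section 4.2 gives the comparator as "crystalloid (0.9% sodium chloride [normal saline]) resuscitation (standard care").

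**The concern.** A treatment-by-subgroup interaction asks whether the PHBP versus crystalloid effect differs between two kinds of participant. Both kinds must exist in both arms. Blood age is a property of the product given in one arm, and the SAP derives it in that arm only. The model that section 9.9 requires therefore has no control data at either level, and half of the D9 block has nothing to hold.

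The SAP names no alternative, so the analyst would have to invent one after the data are in. The two obvious workarounds are to compare each PHBP age class with all controls, or to compare the classes within PHBP. Both are possible, but neither is a randomised subgroup effect. Printed in D9 next to true interactions, and with a direction of effect stated beforehand, either could be over-read.

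The date formula is a second, simpler fault: a unit is bled before it is given, so the stated difference cannot be a positive age.

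**Working it through.** The SAP states no figure on this point, so there is none to reproduce. Two checks and one illustration follow.

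**1. Sign of the age formula (section 9.4).** Take units bled 0, 3, 7, 8, 9, 20 and 35 days before randomisation.

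- As written (date bled minus date of randomisation): 0, −3, −7, −8, −9, −20, −35. None is 8 or more.
- Reversed (date of randomisation minus date bled): 0, 3, 7, 8, 9, 20, 35. The last four are classed as 8 days or older, as intended.

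**2. Can the interaction be estimated?** Let T = 1 for PHBP and S = 1 for the ≥8 days class. The model has an intercept, T, S, T×S and three indicators for the four IDS named in Appendix D2, which makes seven columns. The check used 490 simulated participants allocated 1:1.

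| Coding of crystalloid participants | Consequence | Rank (of 7) |
|---|---|---|
| Ordinary baseline subgroup, both levels in both arms (reference case) | none | 7 |
| All coded <8 days | S equals T×S | 6 |
| All coded ≥8 days | S − T×S equals 1 − T | 6 |
| Missing, so dropped | T equals the intercept; S equals T×S | 5 |
| Literal formula, everyone <8 days | S and T×S are all zero | 5 |
| Literal formula, crystalloid dropped | as above, and T equals the intercept | 4 |

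The rows that code or drop the controls without using the literal formula already take blood age as intended, so correcting the sign does not rescue the interaction. Removing PHBP participants who received no unit does not help either, because the redundancy comes from the control arm.

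The workaround using all controls shows the same thing. Let p₁ and p₂ be the PHBP event risks in the <8 and ≥8 days classes, and p₀ the risk in all controls. The two unadjusted relative risks are p₁/p₀ and p₂/p₀. Their ratio, which is what an interaction measures, is (p₁/p₀)/(p₂/p₀) = p₁/p₂. The controls cancel, leaving a comparison within PHBP that randomisation does not protect.

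**3. The any-unit rule.** If each unit has chance q of being at least 8 days old and ages are independent, a participant given k units gets the ≥8 days label with probability 1 − (1 − q)^k. The SAP gives no q, so these values are assumptions. For k = 2:

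- q = 10%: 1 − 0.9² = 19%
- q = 50%: 1 − 0.5² = 75%
- q = 90%: 1 − 0.1² = 99%

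If the units in a pair of boxes share the same age, the chance stays at q. The label is therefore never less likely with an extra unit, but the size of any increase cannot be read from the SAP.

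**The case against.** The strongest reply is that little is at stake. Section 9.9 treats all subgroup results as exploratory. If the model cannot be fitted, the introduction and Appendix A require the deviation to be reported and justified. The likely result is an empty block in one table, not a wrong trial conclusion. That stands, and it limits the weight of the point. It does not make the written analysis feasible.

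On the formula, the intent is plain: the quantity is called an age, the next sentence speaks of units 8 days or older, and section 9.9 contrasts fresher with older blood. A reader might infer that the reported ≥8 days class will be empty. That is only the literal reading. A column of negative ages would be noticed at once, so this is a wording error to correct and not a forecast of the result. Nor would every PHBP participant fall in the <8 days class even then: Appendix D4 allows for participants given no unit, and they have no age and no stated class.

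Two further inferences go beyond the document:

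- **LyoPlas age would drive the classification.** The rule does refer to blood products in general, while the rationale concerns oxygen carriage. The SAP does not show whether a bleeding date is recorded for LyoPlas, so this is an ambiguity at most.
- **Blood age is strongly confounded by severity.** Section 4.6 has the boxes packed before the patient is met, so severity does not select the stock. It can enter through the number of units given, which section 9.9 itself treats as a stand-in for blood loss. The size of that effect is unknown.

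**Conclusion.** The point holds in two parts. The main one is that blood age has no counterpart in the crystalloid arm. The interaction required by section 9.9, and the crystalloid counts, level-specific relative risks and interaction p-value in D9, cannot be produced for this subgroup. This follows from the structure of the data and rests on no numerical assumption beyond the SAP giving controls no age class, and it gives none. The lesser part is the reversed subtraction, which is wrong as written but obvious in intent.

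The any-unit rule is a caution about interpretation and not a separate error.

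The reach is one of twelve exploratory subgroups. The primary analysis, the secondary outcomes and the sample size are untouched, and nothing here supports a wider doubt about the trial's main result.

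**What to change.** 1. Remove age of blood products from the interaction analyses in section 9.9 and from Appendix D9.
2. Report it instead as an exploratory comparison of the two age classes among PHBP participants who received at least one unit, adjusted for IDS and labelled as non-randomised.
3. In section 9.4, define age as date of randomisation minus date bled.
4. State that, under the any-unit rule, the comparison may be confounded by the number of units received.
5. Optionally, restrict the derivation to PRBC, to match the oxygen-carrying rationale. Other definitions, such as first, oldest or mean unit age, are also defensible provided one is fixed before the data are examined.

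The cost is a few lines in sections 9.4 and 9.9 and one block in D9. No new data are needed.
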